PAatient-CenTric Chronic Pancreatitis Registry (PACT-CP)

PROTOCOL

Protocol ID: NES-EPI-100
Version Number: 3.0
Version Date: 13 April 2021

Study Type: Non-Interventional
Sponsor: Nestlé Health Science USA

Notice of Confidentiality

This document contains confidential information belonging to HealthiVibe, a division of CorEvitas, LLC. Except as otherwise agreed to in writing, by accepting or reviewing this document, you agree to hold this information in confidence and not copy or disclose it to others (except where required by applicable law) or use it for unauthorized purposes. In the event of any actual or suspected breach of this obligation, HealthiVibe must be promptly notified.

PROTOCOL SYNOPSIS

Protocol ID	NES-EPI-100	Sponsor	Nestlé Health Science USA
Study Title	PACT-CP		

Study Objective & Specific Aims

The main objective of this study is to generate real-world evidence reflecting the experience of individuals with exocrine pancreatic insufficiency (EPI) due to chronic pancreatitis (CP). Efforts will be directed toward understanding the unmet need and therapeutic burden to identify the most critical factors that influence treatment choices/prescribing patterns, quality of life, and healthcare utilization outcomes in standard of care for individuals with EPI due to CP. This study has the following specific aims:

1. Create a cohort of well-characterized patients with EPI due to CP for participation in retrospective and prospective research
2. Collect clinical data to characterize both the EPI due to CP disease history and disease progression through a combination of retrospective and prospective collection of medical history, comorbidities, and treatment approaches aimed at increasing the level of understanding of a heterogeneous condition such as EPI
3. Collect data on the differing clinical care practices for patients with EPI to better understand the impact of those patterns on outcomes (including quality of life, comorbidities, and treatments)
4. Collect data on treatment compliance that may impact the EPI due to CP disease experience and/or outcome
5. Collect baseline and longitudinal participant-reported outcome (PRO) data on abdominal pain, gastrointestinal (GI) symptoms, dietary habits, health-related quality of life, depression/anxiety, and PERT use and treatment satisfaction to evaluate the impact of EPI on individuals' health and daily life
6. Gather data on healthcare utilization to be combined with clinical data to generate evidence for the impact and burden of EPI due to CP in this cohort on the healthcare system.

Study Design

This is a prospective, non-interventional research study for individuals diagnosed with EPI due to CP under the care of a gastroenterologist. Target enrollment is approximately 400 individuals, to be recruited over a period of 24 months. The study duration from enrollment to closeout will be five (5) years. Approximately 20 clinical gastroenterology practices in the United States will be contracted to participate.

Eligibility Criteria

To be eligible for the study, study participants must meet all the inclusion criteria and none of the exclusion criteria at the time of enrollment.

Inclusion criteria

To be eligible for enrollment, a study participant must meet the inclusion criteria below:

1. At least 18 years of age (or age of majority)
2. Willing to provide consent to participate
3. Meet ONE (1) of the following at the time of enrollment:
 - a. Diagnosis of chronic pancreatitis (CP)
 - b. Diagnosis of recurrent acute pancreatitis (RAP)

4. Suspected or confirmed diagnosis of EPI made by a healthcare provider
5. On pancreatic enzyme replacement therapy (PERT), either prior to the Enrollment Visit or newly prescribed at the time of the Enrollment Visit.

Exclusion criteria

To be eligible for enrollment into the registry, a study participant must not meet any of the criteria below:

1. Currently participating in or planning to participate in a double-blind randomized trial and/or open-label Phase 3b/4 on CP or EPI
2. Diagnosed with any of the following conditions at the time of enrollment:
 - a. Cystic fibrosis
 - b. Fibrosing colonopathy
 - c. A history of or current diagnosis of pancreatic cancer, main duct papillary mucinous neoplasms (IPMNs), and other pancreatic malignancies
 - d. Allergy to pork or other porcine pancreatic enzyme products (PEPs)
 - e. Any condition that would, in the investigator's opinion, limit the individual's ability to complete the study.

Study Procedures

Study data will be collected from Investigators at the time of routine clinical encounters, as well as from study participants remotely in between routine visits.

Enrollment

Study participants will be enrolled in the study if they meet eligibility criteria and after they have provided consent to participate. During the Enrollment Visit, the Investigator will confirm eligibility and will provide information on suspected/confirmed EPI diagnosis (date of diagnosis, date of onset of symptoms indicative of EPI, method of EPI diagnosis, if applicable), CP etiology, clinical manifestations of EPI (i.e., GI and nutritional manifestations), medical history (comorbidities, surgical and radiological procedures, endoscopic procedures, and laboratory abnormalities), and current treatment(s). Information collected from the study participant includes demographics, current work status, current insurance coverage, family disease history, weight/height, current over the counter (OTC) herbal/nutritional supplements, healthcare utilization, and participant-reported outcome assessments on abdominal pain, GI symptoms, health-related quality of life, depression/anxiety, and PERT use and treatment satisfaction.

Follow-Up

Follow-up data will be collected from the study participants remotely via electronic data capture (EDC) portal. Every 3 months, study participants will complete assessments on current work status, current insurance coverage, current weight, current OTC herbal/nutritional supplements, and abdominal pain, GI symptoms, and PERT use and treatment satisfaction. Every 6 months, in addition to the assessments completed every 3 months, study participants will also complete assessments on health-related quality of life, depression/anxiety, and healthcare utilization.

The Investigator will provide updates during routine clinical encounters approximately every 6 months or at least 150 days from the last registry visits. Data will be collected on clinical manifestations of EPI, current treatment(s), and active assessment of adverse events/serious adverse events (AEs/SAEs) since last visit. "Early" follow-up visits will be conducted whenever a study participant is prescribed a new PERT product. The Investigator will not complete any assessments if the study participants do not return to the sites for their expected routine clinical encounter.

Study Participant Exit

Study participants exit the study upon withdrawal from the study, lost to follow-up (LTFU), transfer of care to a different gastroenterologist, death, or any other reason resulting in a study participant's exit. The Investigator will document the reason for the exit.

Data Collection

Study participants will be followed prospectively, and data from study participants will be collected at 3-month intervals via EDC portal. Investigators will complete assessments approximately every 6 months at the time of routine clinical encounters. AEs will be collected as part of the study data collection forms. SAEs are to be reported within 24 hours (1 business day) of awareness, whether or not the site learns of the event at the time of a registry follow-up visit.

Data Analysis

Analyses will be guided by the specific aims of the registry. Complete details of all analyses will be described in a standalone Statistical Analysis Plan (SAP) with accompanying mock Tables, Figures and Listings (TFLs). Briefly, all data will be summarized descriptively. Study disposition of all participants will be summarized including dropouts (with reasons presented for those who drop out), and for lost to follow-up (at what point they are lost, and if they return). Multivariate modeling will be employed to analyze clinical data on EPI disease history and disease progression by analyzing patterns of medical history, comorbidities, and treatment approaches. Clinical care practices will be explored with their potential impact on quality of life, comorbidities, and treatments using the same multivariate modeling. Treatment compliance will be examined for each of the models, knowing that biases are introduced with participant recall. Prescribing practices will be descriptively presented (to include type of PERT, dose at initiation and escalation, recommendation on how to take PERT, and reason for switching to another PERT, if applicable). If trends are identified in prescribing patterns, these trends may be further explored. Healthcare utilization data will be assessed with key variables from the clinical dataset.

Confounding will be assessed for predicting outcomes with the registry data. If any confounding is identified, statistical procedures may be employed as appropriate for that confounder and outcome. Given that groupings within a study population may exist, these potential grouping effects will be handled with use of ANOVA (analysis of variance) models. Data quality assessed in terms of missing data, out of range values, and completeness will be presented, as to allow for appropriate interpretation and extrapolation of the study results.

PROTOCOL SIGNATURE PAGE

Investigator Agreement

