7.5.1 Abdominal Pain

Multiple constructs will be measured for abdominal pain, which will be collected with single-item questions around the abdominal pain pattern (constant vs. episodic), episodic abdominal pain intensity (0 – 10 numerical rating scale), frequency (number of abdominal pain episodes last month), and episode duration over the past month. Additionally, the abdominal pain history (in months), abdominal pain triggers (high-fat meals, stress, alcohol, tobacco, activity, other), abdominal pain relief methods (bowel movement, OTC analgesic medication, rest, fasting/diet adjustment), and abdominal pain control over the past month will be collected. Study participants will also be asked whether the abdominal pain was severe enough to seek medical attention, and if so, when and what type of medical attention they received (primary care provider, specialist, emergency room, urgent care, hospitalization). In the event they were hospitalized, the length of stay will be collected as well.

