8.3 Study Participant Forms

The study participant will complete their assessments at the site during Enrollment and remotely via EDC portal, accessed via a mobile-friendly secure web URL for Follow-Up.

Study personnel are prohibited from completing any part of the Study Participant forms on behalf of the study participant. However, study personnel are allowed to assist the study participant in the event of issues with the electronic device and can show the study participant where the data should be entered. If a study participant requests assistance during the visit, study personnel are permitted to facilitate completion of the form by transcribing the study participant's verbal responses to the Study Participant Form. At Enrollment, study participants will undergo a training on how to complete their assessments remotely via EDC portal for Follow-Up.

Site personnel are expected to review the study participants' responses for completeness, and to follow-up on any information captured in the forms. Details regarding any AEs occurring in the study participant and reported in the Study Participant Form must also be transcribed to the Investigator Form.

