9. SAFETY REPORTING

9.1 Adverse Events

An AE is defined as any untoward medical occurrence in a study participant administered a pharmaceutical product and which does not necessarily have to have a causal relationship with the treatment. AE data collection

begins *after* a study participant has completed an Enrollment Visit. During the Follow-Up on-site visits, the Investigator and/or designee is required to question the study participant regarding the occurrence of AEs since the previous registry visit. Pertinent details regarding any reported AEs are to be captured using the pertinent sections in the Investigator Follow-Up forms.

Any AEs that are reported by the study participant, discovered as a result of general questioning by the Investigator, should be recorded in the Investigator Follow-Up Form at the next scheduled registry visit following the onset of the event.

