9.2 Serious Adverse Events

SAEs are defined as adverse events that result in any of the following outcomes:

- Hospitalization (new or prolongation)
- Death
- Immediately life threatening (urgent intervention required to prevent outcome of death)
- Persistent/significant disability or incapacity
- Congenital abnormality or birth defect
- Otherwise serious (important medical event) in the opinion of the Investigator (i.e., event that may jeopardize the study participant and require medical or surgical intervention/treatment to prevent one of the other outcomes listed above).

SAEs are to be reported by sites in accordance with registry AE Reporting Guidelines as soon as possible after the site learns of the event (within 1 business day), via the electronic data capture system or approved backup mechanism (per the AE Reporting Guidelines). These events should also be captured by the Investigator at the next registry visit following the onset date of the event. Sites are required to request supporting documents (e.g., hospital records, laboratory results, etc.) for each SAE. These records should be submitted as soon as they become available to the site (between registry visits). The Investigator or qualified designee must remove all of the study participant's personal identifiers from the supporting documents prior to submission to HealthiVibe.

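### Nothing carries a portal-reported hospitalization to the site as a possible SAE, and the reporting rules conflict for participants who miss clinic

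*Protocol*

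**What the plan says.** Two sets of rules bear on SAE capture.

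**Visit-based rules.** The synopsis (Follow-Up) and SAP 3.1 list the data that the Investigator supplies at routine encounters, including active assessment of AEs and SAEs. The paragraph ends: "The Investigator will not complete any assessments if the study participants do not return to the sites for their expected routine clinical encounter". Protocol 9.1 says that AEs "should be recorded in the Investigator Follow-Up Form at the next scheduled registry visit following the onset of the event". Table 1 marks AEs only in the on-site follow-up column.

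**Rules that do not need a visit.** The synopsis (Data Collection) requires SAE reports within 1 business day of awareness, "whether or not the site learns of the event at the time of a registry follow-up visit". Protocol 9.2 requires them "as soon as possible after the site learns of the event (within 1 business day), via the electronic data capture system". Protocol 8.3 expects site personnel to review participants' responses and follow them up, and adds: "Details regarding any AEs occurring in the study participant and reported in the Study Participant Form must also be transcribed to the Investigator Form".

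**What participants report.** The abdominal pain items, asked every 3 months, include medical attention sought for pain: "In the event they were hospitalized, the length of stay will be collected as well". The healthcare utilization items, asked every 6 months, include hospitalizations and length of stay (7.4, Table 1). Both are completed remotely after Enrollment.

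**What is analyzed.** SAP 5.7 tabulates SAEs by term. SAP 5.8 and 5.13 summarize participant-reported hospitalization. The SAP text describes no cross-check between these sources.

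**The concern.** An adverse event that leads to hospitalization is an SAE under 9.2. The registry asks participants about hospitalization several times a year through a channel that does not depend on clinic attendance. If the Investigator is told to complete nothing when a participant does not attend, and no rule moves the portal answer to the site, the database can hold evidence of an SAE that never becomes an SAE record.

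SAE capture would then depend partly on attendance, and the shortfall would fall on participants followed only through the portal. A participant could appear as hospitalized in the pain or utilization summaries with no matching entry in the SAE listing, and the plan has no step that would bring this to light before database lock.

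**Working it through.** The documents state no hospitalization rate, missed-visit rate or SAE count, so the check is mainly a comparison of texts for one case: a participant who answers the portal, does not attend clinic, and is hospitalized for an adverse event after Enrollment.

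1. **Does the participant stay enrolled?** Yes. Protocol 6.4 defines loss to follow-up by 2 consecutive missed remote timepoints. Missed clinic visits are not an exit reason, and 6.3.2 only encourages the site to reschedule.

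2. **Is the event an SAE?** Yes, in this case. Section 9.2 reads "SAEs are defined as adverse events that result in any of the following outcomes", and hospitalization heads the list. The adverse event is essential: a planned admission need not qualify. Hospitalizations reported at Enrollment do not qualify either, because AE collection begins after that visit (9.1).

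3. **Does the portal record it as an AE?** No. Table 1 lists no AE item among participant-provided data. The hospitalization appears under abdominal pain or healthcare utilization. The utilization item, as described in 7.4, records number and length of stay but no reason. The transcription duty in 8.3 applies to AEs, so staff must first recognize the entry as one.

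4. **Does the entry reach the site?** Protocol 8.3 expects site review but gives no trigger or deadline. Late remote forms are chased by the Registry Manager (6.3.1), not the site. Neither document provides an alert.

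5. **Does the 1-business-day clock start?** It starts when the site learns of the event. Neither document says whether a portal entry is site awareness.

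6. **Where would the event be written down?** If 8.3 is followed, on the Investigator Form. But 9.1 ties the Follow-Up Form to the next registry visit, and the synopsis sentence, read literally, bars Investigator assessments without one. The SAE route in 9.2 stays open, but only once the site is aware.

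7. **What if the participant does return?** Protocol 6.3.2 says that the follow-up forms should cover the time since the last registry visit, so a later visit can pick up the event. If that visit is the first the site hears of it, the delay for a visit inside the Table 1 window (180 days, plus or minus 30) can reach 180 + 30 = 210 days, for an event just after the previous visit. After a missed visit the delay has no stated limit.

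8. **Would the analysis show the gap?** The seriousness criterion, including hospitalization, is collected for each SAE (7.2, SAP 5.7), so matching by participant is feasible. The SAP text does not plan it.

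**The case against.** The strongest reply is that SAE reporting does not depend on a visit at all. The synopsis and 9.2 tie it to site awareness. Section 9.2 says that SAEs are also to be captured at the next visit, which makes the prompt report a separate act. Table 1 names a distinct SAE form, and 7.2 has a report status for SAEs already reported between visits. In context, the sentence barring assessments follows the list of on-site data and can be read as covering only the visit forms. Section 8.3 makes transcription of AEs mandatory. Section 9.2 also refers to separate AE Reporting Guidelines, which may set review times, and the table and listing templates are in another document.

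Much of this stands. It rules out the reading that the Investigator completes no form of any kind unless the participant returns. It also means that a missed visit does not by itself lose an event, because 6.3.2 lets a later visit cover the gap.

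It does not close the gap. AE/SAE assessment is named in the same paragraph as the bar, so a site could reasonably take it to be included. Every awareness-based rule presupposes awareness, and nothing in the two documents links a portal answer to it. The between-visit status allows such reports but does not prompt them. The provision in 6.4 for AEs after the last visit applies only when exit is due to death.

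A reader might also infer that the report will show two hospitalization counts that disagree. The documents do not support this. SAP 5.7 plans no count by the hospitalization criterion, so there is no second count to compare with 5.13. Differences could also arise from definitions and time windows alone.

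**Conclusion.** The point holds as a conflict between rules and a missing link. The visit-based sentences (synopsis Follow-Up, SAP 3.1, 9.1, Table 1) need reconciling with the awareness and transcription rules (synopsis Data Collection, 8.3, 9.2). A hospitalization for an adverse event after Enrollment may be reported late. It may be missing from the SAE tables if the participant does not return and nobody follows up the portal entry.

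The extent cannot be estimated from the documents. It is tempting to set the understatement equal to the share of participants who miss visits. That would treat a missed visit as permanent non-return and assume that no site ever learns of an event another way; the documents support neither assumption. Nor is every portal-reported hospitalization an SAE.

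The correction should be made, but it does not threaten the main results: none of the six specific aims is a safety aim, and the SAE analyses are descriptive. The conclusion assumes that the separate AE Reporting Guidelines do not already define portal entries as awareness or set a review time. If they do, part of the fix reduces to a cross-reference.

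**What to change.** (a) In the synopsis (Follow-Up) and SAP 3.1, exempt AE/SAE reporting from the sentence that stops Investigator assessments. Reword 9.1 so that it agrees with the synopsis (Data Collection), 8.3 and 9.2.

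(b) Have the EDC send the site a query when a post-Enrollment portal form reports a hospitalization. State that receipt of the query is site awareness under the existing 9.2 rule. The site then completes the SAE form or closes the report with the not-an-event or duplicate status that 7.2 already provides.

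(c) In SAP 5.7, add a participant-level listing, run before database lock, of portal-reported post-Enrollment hospitalizations with no matching SAE.

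The cost is a few sentences in the protocol and SAP, one EDC check and one listing. The downside is that sites will answer some queries about planned or duplicate admissions. No new data need be collected from participants.

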1. BACKGROUND

Exocrine pancreatic insufficiency (EPI) is a condition caused by reduced or inappropriate secretion or activity of pancreatic juice and its digestive enzymes, and pancreatic lipase in particular. EPI can result in clinical manifestations such as steatorrhea, weight loss, and biochemical alterations related to lipids and liposoluble micronutrients malabsorption and maldigestion (Perbtani & Forsmark, 2019). While overt maldigestion is associated with easily detectable symptoms and impact on quality of life (Johnson et al., 2017), long-term malnutrition can have significant detrimental consequences on overall health, as well as increased risk of mortality in patients with chronic pancreatitis (CP) due to cancer, infections, and cardiovascular events (de la Iglesia-Garcia et al., 2018). Thus, it is important that EPI is diagnosed early and treated appropriately to alleviate symptoms and reduce the risk of long-term complications associated with EPI; however, EPI symptoms and manifestations are not specific and are often shared with other common gastrointestinal (GI) conditions. This can lead to a lack of recognition in many individuals with EPI. Even in those who are correctly diagnosed, many are not treated with appropriate dosages of pancreatic enzyme replacement therapy.

The prevalence of EPI in the general population is unknown. It is most often associated with diseases of the exocrine pancreas, being a common late-stage manifestation of CP. CP is a disorder characterized by ongoing pathological pancreatic inflammation, leading to fibrosis and eventually to the loss of both endocrine and exocrine function. EPI typically develops after 5 – 10 years of CP, requiring approximately 90% of the endogenous pancreatic enzyme secretion to be lost (C. E. Forsmark, 2013). The risk of EPI varies with the underlying etiology of CP, with the highest risk population being those with chronic alcohol use (Ammann et al., 1987). Smoking has an independent effect on the development of CP, and the probability of EPI increases when tobacco exposure is combined with alcohol (Luaces-Regueira et al., 2014). In addition, EPI can also occur following severe acute pancreatitis (AP) as a result of loss of pancreatic parenchyma and functional capacity due to significant amounts of pancreatic necrosis (Hollemans et al., 2018), or recurrent acute pancreatitis without the overt presence of CP at the time of evaluation. Other causes for EPI are pancreatic malignancies (Sikkens et al., 2014) and resective pancreatic surgeries such as pancreatic duodenectomy (Goess et al., 2016) and distal pancreatectomy (Okano et al., 2016). EPI is also observed in other conditions, such as cystic fibrosis (Singh & Schwarzenberg, 2017), diabetes (Mohapatra et al., 2016), inflammatory bowel disease (Maconi et al., 2008), and GI surgeries (Antonini et al., 2018; Huddy et al., 2013; Straatman et al., 2017).

The diagnosis of EPI is best made by a combination of clinical history, ruling out other causes of malabsorption, cross sectional imaging of the pancreas, and diagnostic tests. The most practical approach involves diagnostic procedures that are noninvasive, inexpensive, and readily available. Such available lab tests are indirect measures of pancreatic function and include fecal elastase-1 (FE-1) test, fecal fat measurement, and fat-soluble vitamin measurements. These tests are generally less expensive and easier to perform compared to direct pancreatic functional tests.

Treatment of EPI relies on pancreatic enzyme replacement therapy (PERT). Pancrelipase formulations available in the United States are enteric coated (brand names: Creon®, Pancreaze®, Pertzye®, and Zenpep®) and non-enteric coated (brand name: Viokase®). Enteric coating prevents the enzymes from being denatured by gastric acid and the coating dissolves in the duodenum. All available formulations are derived from porcine origin. Finding the ideal dosing of PERT for a particular patient can be challenging because the response to treatment is variable from patient to patient. In general, enteric coated formulations are preferred because of gastric acid protection. Multiple studies have estimated that at least 30,000 IU (or about 90,000 USP units) of lipase delivered to the intestine with each meal should eliminate steatorrhea (Forsmark et al., 2002; Imrie et al., 2010; Keller & Layer, 2005). This amount represents approximately 10% of normal pancreatic secretion (Shandro et al., 2018). The goal is not to

replace 100% of estimated pancreatic function since steatorrhea only develops in severe disease. Therefore, starting doses should be between 30–40,000 IU with every meal and 15–20,000 IU with snacks (Imrie et al., 2010; Keller & Layer, 2005; Shandro et al., 2018). Patients should be instructed to take ½ the total dose with the first bite of the meal and other ½ either during the meal or at the end of the meal. In clinical practice, the choice of formulation will also be determined by cost and insurance coverage of the individual patient. In addition to PERT, lifestyle changes are paramount in the management of EPI. All patients should be counseled to stop smoking and drinking alcohol. Diet changes such as a healthy balanced diet and more frequent, smaller meals can also alleviate symptoms.

The benefits in treatment of EPI have led to practice guideline recommendations for the use of PERT in patients with CP, pancreatic cancer, and pancreatic surgery (Sabater et al., 2016). However, studies suggest that the majority of patients are either not treated or treated with inadequate dosages. In a European survey study of patients with EPI due to CP or pancreatic cancer, one-quarter of patients took three or fewer capsules a day and more than two-thirds of patients reported ongoing symptoms of steatorrhea (Sikkens et al., 2012b). Similarly, in a Dutch national survey of patients with CP and EPI, the median initiating daily dosage was suboptimal (four capsules daily, 25,000 USP units of lipase each), and a majority of patients reported ongoing gastrointestinal symptoms of EPI including steatorrhea and weight loss (Sikkens et al., 2012a). More recently, in a US population-based analysis, 6.5% of patients with CP received any testing for EPI, 30.4% received a prescription for PERT, and only 10% received a minimally effective dose (Forsmark et al., 2017a). Likewise, in a similar analysis of patients with pancreatic cancer, only 1.9% of patients had testing for EPI and 22% received a prescription for PERT, with only 5.5% receiving an adequate dose (Forsmark et al., 2017b). Ultimately, these studies highlight that diagnostic testing is rarely performed, treatment with PERT is infrequent, and, if utilized, the dosage amounts are generally inadequate.

In order to better study the disease journey and the effectiveness and safety of available therapies for EPI, databases and registries are needed. To date, however, there have only been a few observational studies conducted on EPI. These existing databases are limited as they lack measures that could advance the understanding of the disease, comorbidities, disease progression, risk and/or mitigating factors. In addition, these studies do not provide a comprehensive assessment of existing treatments. This observational study with geographical representation across the United States will be well positioned to address the above-mentioned issues by collecting a comprehensive set of real-world data around disease and treatment outcomes.

